6.1.1. General Considerations for Analyses during the Blinded Treatment Dosing Period (Period 2)

Comparisons between each ixekizumab regimen (80 mg Q2W or 80 mg Q4W) and placebo, as well as comparisons between adalimumab and placebo, will be performed for all analyses in Period 2.

Period 2 starts at the first injection of study treatment at Week 0 (Visit 2) and ends prior to the first injection of study treatment at Week 16 (Visit 8) or the ETV (between Weeks 0 and 16).

Baseline will be defined as the last available value before the first injection for efficacy, health outcome, and safety analyses. In most cases, this will be the measure recorded at Week 0 (Visit 2). For efficacy measures, if the patient does not take any injection, the last available value on or prior to randomization date will be used. Change from baseline will be calculated as the visit value of interest minus the baseline value. For safety analyses using a baseline period, the baseline period is defined as the time from Visit 1 to the date/time of the first injection.

The randomization to treatment groups is stratified by country and baseline CRP status (nonelevated versus elevated) as described in Section 5.2. The countries will be categorized into geographic regions for analysis. Geographic regions are defined in Section 6.2. Unless otherwise specified, the statistical analysis models will adjust for geographic region and baseline CRP status.

Unless otherwise specified, treatment groups of ixekizumab 80 mg Q2W and Q4W will be analyzed without regard to starting dose.

The primary analysis method for treatment comparisons of categorical efficacy and health outcome variables at specific time points will be made using a logistic regression analysis with treatment, geographic region (Europe and non-Europe), and baseline CRP status in the model using PROC Logistic with a Wald test. The odds ratio and 95% CIs will be reported; treatment difference and 95% CI will also be reported. Secondary analysis will be conducted using a Fisher's exact test. In the case when logistic regression model does not produce statistical results due to sparse data, Fisher's exact test will be used.

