the within-patient errors will be unstructured. The REML will be used. The Kenward-Roger method will be used to estimate the denominator degrees of freedom. Type III tests for the least-squares (LS) means will be used for the statistical comparison; the 95% CI will also be reported. Treatment group comparisons with placebo at Week 16 (Visit 8) and all other visits will be reported. If the unstructured covariance matrix results in a lack of convergence, the similar approach specified above for categorical MMRM will be used.

For the analysis of CRP, the MMRM model will include treatment, geographic region, baseline CRP status, visit, and treatment-by-visit interaction as fixed factors. Note for the ratio of postbaseline to baseline in CRP, analysis will be performed on the natural log transformed ratio.

When the ANCOVA is used, the model will include treatment, geographic region, baseline CRP status, and baseline value (except for the analysis of CRP, see paragraph below). Type III sums of squares for the LS means will be used for the statistical comparison; the 95% CI will also be reported.

For the analysis of CRP, the ANCOVA model will include treatment, geographic region, and baseline CRP status. Note for the ratio of postbaseline to baseline in CRP, analysis will be performed on the natural log transformed ratio.

For the analysis of ASDAS disease activity states (ie, inactive, moderate, high, and very high disease states), the repeated measures proportional odds model will include treatment, geographic region, baseline CRP status, visit, and treatment-by-visit interaction.

The impact of ixekizumab starting dose of 160 mg versus 80 mg on treatment response at Week 16 and time to onset of action will be summarized and evaluated. Response rates in categorical variables (including ASAS40, ASAS20, ASDAS major improvement) and LS mean change in continuous efficacy measures (including CRP, BASFI) at Week 16 will be presented for patients randomized to ixekizumab Q2W or Q4W treatment regimen with ixekizumab 160 mg starting dose and with ixekizumab 80 mg starting dose.

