6.17. Planned Exploratory Analyses

- To assess the psychometric properties (including reliability, validity, and responsiveness) of the Fatigue NRS in ITT Population.
- To assess the psychometric properties (including reliability, validity, and responsiveness) of the ASAS-HI in ITT Population.
- To explore the impact of each ixekizumab regimen on change from baseline in measures of health utility (EQ-5D); and healthcare resource utilization in the double-blind dosing period and throughout the Extended Treatment Period in the ITT Population.

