6.17.4. Planned Exploratory Health Outcome/Quality-of-Life Analyses

[Table RHBV.6.14](#) includes the description and derivation of the exploratory health outcomes and QOL measures.

[Table RHBV.6.15](#) provides the detailed analyses including analysis type, method and imputation, population, time point, and treatment group comparisons for the exploratory health outcomes and QOL analyses.

Table RHBV.6.14. Description and Derivation of Exploratory Health Outcomes and Quality-of-Life Measures

Measure	Description	Variable	Derivation / Comment	Missing Items
European Quality of Life – 5 Dimensions 5 Level	
EQ-5D-5L: is a standardized measure of health status used to provide a simple, generic measure of health for clinical and economic appraisal. The EQ-5D-5L consists of 2 components: a descriptive system of the respondent’s health and a rating of his/her current health state using a 0- to 100-mm VAS. The descriptive system comprises the following 5 dimensions:
 
 item 1: mobility item 2: self-care item 3: usual activities item 4: pain/discomfort item 5: anxiety/depression 
The respondent is asked to indicate his/her health state by ticking (or placing a cross) in the box associated with the most appropriate statement in each of the 5 dimensions.
	
EQ-5D mobility, EQ-5D self-care, EQ-5D usual activities, EQ-5D pain/ discomfort, EQ-5D anxiety/ depression
	
Five health profile dimensions, each dimension has 5 levels: 1 = no problems 2 = slight problems 3 = moderate problems 4 = severe problems 5 = extreme problems
 
It should be noted that the numerals 1 to 5 have no arithmetic properties and should not be used as a primary score.
	
Each dimension is a single item, missing if missing.

		
EQ-5D-5L UK Population-based index score
	
Uses the concatenation of the value of each EQ-5D-5L dimension score in the order: item1; item2; item3; item4; item5. Derive EQ-5D-5L UK Population-based index score according to the link by using the UK algorithm (Szende et al. 2007) to produce a patient-level index score between -0.59 and 1.0 (continuous variable): http://www.euroqol.org/fileadmin/user_upload/Documenten/Excel/Crosswalk_5L/EQ-5D-5L_Crosswalk_Value_Sets.xls
	
If any of the items is missing, the index score is missing

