	
The VAS records the respondent’s self-rated health on a vertical VAS where the endpoints are labeled 100 = “best imaginable health state” and 0 = “worst imaginable health state”.
	
EQ-5D VAS
	
Range from 0 = “worst imaginable health state” to 100 = “best imaginable health state”. Note: higher value indicates better health state.
	
Single item, missing if missing

Healthcare Resource Utilization	
Healthcare resource utilization data regarding the number of visits to medical care providers, such as general
	
Visits to medical care providers (except hospitals)
	
Derivation will be performed within each treatment period
	
NA

		
Days in hospital
		

Measure	Description	Variable	Derivation / Comment	Missing Items
	practitioners, specialists, physical, or occupational therapists, and other nonphysical care providers for services outside of the clinical trial; emergency room admissions; hospital admissions; and concomitant medications will be recorded by the investigator in the study's CRF.	Number of hospital admissions (Medical ICU, surgical ICU, coronary ICU, general ward, trauma unit, unknown or other)		
		Healthcare providers (type of specialist for healthcare practitioner)		

Abbreviations: EQ-5D-5L = European Quality of Life – 5 Dimensions 5 Level; ICU = intensive care unit; UK = United Kingdom; VAS = visual analog scale.

Table RHBV.6.15. Description of Exploratory Health Outcomes and Quality-of-Life Analyses

Measure	Variable	Analysis Method (Sections 6.1 and 6.3)	Population (Section 6.1.5)	Comparison / Time Point
EQ-5D-5L	EQ-5D mobility, EQ-5D self-care, EQ-5D usual activities, EQ-5D pain/discomfort, EQ-5D anxiety/depression	For each EQ-5D dimension, the proportion of patients with “no problems” will be analyzed by: Logistic regression analysis with NRI; Fisher’s exact test with NRI	ITT Population	IXE80Q2W & IXE80Q4W vs. placebo at Week 16
		Descriptive statistics of each category and proportion of patients with “no problems”	Extended Treatment Period Population	IXE80Q2W & IXE80Q4W during Period 3
	Change from baseline in: EQ-5D-5L UK Population-based index score, EQ-5D VAS	ANCOVA with mBOCF	ITT Population	IXE80Q2W & IXE80Q4W vs. placebo at Week 16
		Descriptive statistics of change from baseline	Extended Treatment Period Population	IXE80Q2W & IXE80Q4W during Period 3

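### Each EQ-5D-5L dimension is compared with placebo at Week 16 only as 'no problems' versus any problem, so a shift among the four problem levels cannot show in that dimension's test; the likely power loss is large for pain/discomfort and smaller elsewhere

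*SAP*

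**What the plan says.** EQ-5D is exploratory. SAP Section 6.17 sets the aim: "To explore the impact of each ixekizumab regimen on change from baseline in measures of health utility (EQ-5D"). Each dimension has five levels, from no problems to extreme problems (SAP Table RHBV.6.14; Protocol Section 8.1.3.1).

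Table RHBV.6.15 then plans:

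- **Dimensions, Week 16, ITT, each ixekizumab regimen against placebo.** "For each EQ-5D dimension, the proportion of patients with “no problems” will be analyzed by" two methods: "Logistic regression analysis with NRI", and Fisher's exact test with the same imputation. Under SAP Section 6.1.1 the logistic model is a "logistic regression analysis with treatment, geographic region (Europe and non-Europe), and baseline CRP status in the model". The patient's baseline level on the dimension is not a covariate.
- **Dimensions, Period 3.** "Descriptive statistics of each category and proportion of patients with" 'no problems'. By then every patient is assigned to ixekizumab and no between-group comparison is made (Table RHBV.6.2).
- **Index and VAS, Week 16, ITT.** "Change from baseline in: EQ-5D-5L UK Population-based index score, EQ-5D VAS", by ANCOVA with mBOCF. The index is built from all five levels: "Uses the concatenation of the value of each EQ-5D-5L dimension score in the order: item1; item2; item3; item4; item5".

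Elsewhere the SAP does use an ordinal model. For the four ASDAS disease activity states, "the repeated measures proportional odds model will include treatment, geographic region, baseline CRP status, visit, and treatment-by-visit interaction" (Section 6.1.1).

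**The concern.** The dimension test cuts a five-level scale at its best level. Within that test:

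- a move from extreme to slight problems counts as nonresponse, exactly like no change;
- a patient with no problems at both visits counts as a success, although the aim is change from baseline, and the model has no baseline level to correct for this;
- where few patients can reach 'no problems', the cut falls at the sparse end of the scale and discards most of the information.

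The third point is likely to apply to pain/discomfort. Protocol inclusion criterion [3] requires BASDAI and total back pain of at least 4 at screening and at baseline, and complete absence of pain or discomfort 16 weeks later is a demanding target. No five-level table by arm is planned at Week 16, so a reader could not see a shift that the binary test missed. What is at stake is a misleading 'no difference' on a single exploratory dimension, not any primary or major secondary claim.

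**Working it through.** **1. The plan's own power figure.** SAP Section 5.3: 80 per arm, 44% against 16% for ASAS40, two-sided Fisher's exact test at 0.05, about 96% power. Exact enumeration gives 96.7%, so it reproduces. It concerns ASAS40 only; no power is stated for EQ-5D.

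**2. Inputs for the dimensions.** From the plan: 80 per arm; Fisher's test is one of the two planned methods. Taken for illustration: two-sided 0.05. Assumed, because neither document gives an EQ-5D distribution or effect: placebo percentages in levels 1 to 5 at Week 16, and a common odds ratio (OR) of 2.0 or 2.5 at every cut.

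| 'No problems' on placebo | Levels 1 to 5 (%) |
|---|---|
| 2% | 2, 20, 43, 30, 5 |
| 5% | 5, 28, 40, 23, 4 |
| 10% | 10, 30, 35, 21, 4 |
| 15% | 15, 33, 33, 16, 3 |

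**3. Formulas.** Active arm: cumulative odds = OR × placebo cumulative odds. Binary power: exact enumeration on level 1 against levels 2 to 5, for Fisher's test and for an unadjusted Wald test of the log odds ratio (Fisher's test if a cell is zero). Ordinal power (Whitehead): Φ(ln OR × √V − 1.96), where V = n₁n₂N / [3(N+1)²] × (1 − Σp̄³) and p̄ is the mean of the two arms' level probabilities.

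**4. One case in full (5%, OR 2.0).** Placebo cumulative proportions 0.05, 0.33, 0.73, 0.96 become 0.095, 0.496, 0.844, 0.980. The binary contrast is 5.0% against 9.5%, and Fisher's power is 12%. For the ordinal test, Σp̄³ = 0.098 and 80 × 80 × 160 / (3 × 161²) = 13.17, so V = 13.17 × 0.902 = 11.87. Then 0.693 × 3.446 − 1.96 = 0.43, and Φ(0.43) = 67%.

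**5. Results.**

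| 'No problems' on placebo | OR | Fisher | Wald | Ordinal |
|---|---|---|---|---|
| 2% | 2.0 | 2% | 2% | 66% |
| 2% | 2.5 | 5% | 6% | 88% |
| 5% | 2.0 | 12% | 15% | 67% |
| 5% | 2.5 | 24% | 28% | 89% |
| 10% | 2.0 | 25% | 30% | 67% |
| 10% | 2.5 | 45% | 52% | 89% |
| 15% | 2.0 | 35% | 40% | 67% |
| 15% | 2.5 | 60% | 65% | 89% |

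A Wilcoxon simulation at 5% and OR 2.5 gave 88%, which supports the ordinal formula.

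Share of ordinal power kept by Fisher's test: at 5%, 12/67 = 18% and 24/89 = 27%; at 15%, 35/67 = 52% and 60/89 = 67%.

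**6. Departures from a common odds ratio.** Placebo 10, 30, 35, 21, 4 throughout.

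- All movement below the cut (active 10, 52, 28, 8, 2): Fisher 3%, Wilcoxon 77%.
- Gain concentrated in 'no problems' (active 30, 25, 25, 16, 4): Fisher 87%, Wilcoxon 64%. Here the planned test is better.

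These calculations omit dropout, nonresponder imputation and covariates.

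**The case against.** The strongest reply is that the improvement is not lost. The index uses the level of every dimension, its change from baseline is tested against placebo at Week 16, and that meets the aim in Section 6.17. Pain and function are also tested on fuller scales: spinal pain, BASFI, the SF-36 domains and WPAI activity impairment. This stands, and it limits the consequence. It does not make the dimension test informative, because the index merges five dimensions and cannot say which one moved.

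Second, the common odds ratio favours an ordinal test, and the level distributions are assumed. This also stands, and step 6 shows the reversal. It argues for keeping the 'no problems' proportion beside an ordinal analysis, not for relying on it alone.

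Third, Protocol Section 8.1.3.1 says that the numerals 1 to 5 lack arithmetic properties and should not serve as ordinal scores; SAP Table RHBV.6.14 says only that they should not be a primary score. A proportional odds model uses the order of the labelled categories and does no arithmetic on the codes, but the SAP should say so.

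A reader might infer that most of the power is lost for usual activities as well as pain. The documents do not support that: they give no distribution for usual activities, the entry criteria do not address it, and at an assumed 15% the planned test keeps about half to two-thirds of the ordinal power. A reader might also infer that a move from extreme to slight problems counts for nothing in the EQ-5D analysis as a whole; the index ANCOVA shows otherwise.

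**Conclusion.** The point holds in a limited form. The only Week 16 placebo comparison of each dimension is 'no problems' against any problem, without the baseline level in the model and without a five-level table by arm. Improvement within levels 2 to 5 cannot register in that test, though it does reach the index.

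Under a common odds ratio of 2.0 to 2.5 with 80 per arm, the cost is severe where 'no problems' is rare: about 2% to 24% power by Fisher's test against 66% to 89%, for an assumed 2% to 5% on placebo. That range is a reasonable guess for pain/discomfort from the entry criteria, but those criteria apply at screening and baseline and do not fix the Week 16 rate. At 15% the loss is moderate, 35% to 60% against 67% to 89%. If all gain is into 'no problems', there is no loss.

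Severity is low: EQ-5D is exploratory, has no power target or multiplicity adjustment, and supports no confirmatory claim.

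**What to change.** In Table RHBV.6.15 keep the 'no problems' proportion and its tests, and add for each dimension at Week 16 in the ITT population:

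1. the five-level distribution by arm;
2. a proportional odds comparison of each ixekizumab regimen with placebo, with treatment, geographic region, baseline CRP status and the baseline level of that dimension. The Schedule of Activities has EQ-5D at Week 0 and Week 16 only within the scheduled Period 2 visits, so a single-visit model is enough;
3. a stated missing-data rule consistent with the ASDAS-state analysis, where Table RHBV.6.4 assigns a missing score to the worst state.

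Add one sentence reconciling this with Protocol Section 8.1.3.1: the model uses the order of the labelled categories and does no arithmetic on the numerals. SAP Version 2 preceded unblinding and Version 3 followed it (SAP Section 3). Anything introduced after Version 2 should therefore be labelled exploratory and added after unblinding, much as the ASDAS <2.1 analysis is marked ad hoc.

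The cost is a few table rows, a short paragraph and five extra exploratory models. No new data are needed. The downside is reliance on the proportional odds assumption, which the five-level table lets a reader judge.

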#### 9.2.1. General Considerations for Analyses during the Blinded Treatment Dosing Period (Period 2)

Comparisons between each ixekizumab regimen (80 mg Q2W or 80 mg Q4W) and placebo, as well as comparisons between adalimumab and placebo, will be performed for all analyses in Period 2.

Period 2 starts at the first injection of study treatment at Week 0 (Visit 2) and ends prior to the first injection of study treatment at Week 16 (Visit 8) or the ETV (between Weeks 0 and 16).

Baseline will be defined as the last available value before the first injection for efficacy, health outcomes and safety analyses. In most cases, this will be the measure recorded at Week 0 (Visit 2). For efficacy measures, if the patient does not take any injection, the last available value on or prior to randomization date will be used. Change from baseline will be calculated as the visit value of interest minus the baseline value. For safety analyses using a baseline period, the baseline period is defined as the time from Visit 1 to the date/time of the first injection.

The randomization to treatment groups is stratified by country and baseline CRP status (nonelevated or elevated) as described in Section 6.2. The countries will be categorized into geographic regions for analysis. Geographic regions will be defined in SAP upon country finalization. Unless otherwise specified, the statistical analysis models will adjust for geographic region and baseline CRP status.

Unless otherwise specified, treatment groups of ixekizumab 80 mg Q2W and Q4W will be analyzed without regard to starting dose.

The primary analysis method for treatment comparisons of categorical efficacy, health outcomes variables at specific time points will be made using a logistic regression analysis with treatment, geographic region, and baseline CRP status in the model. The odds ratio and 95% confidence intervals (CIs) will be reported; treatment difference and 95% CIs will also be reported. Secondary analysis will be conducted using a Fisher's exact test.

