Table RHBV.6.2. Treatment Groups and Comparisons for Each Study Period and Analysis Population

Study Period	Analysis Population	Treatment Group	Abbreviation	Comparison
Blinded Treatment Dosing Period (Period 2)	Intent-to-Treat Population;	Placebo Adalimumab 40 mg Q2W Ixezumab 80 mg Q4W Ixezumab 80 mg Q2W	PBO ADA40Q2W IXE80Q4W IXE80Q2W	ADA40Q2W vs. PBO IXE80Q4W vs. PBO
	Per Protocol Set;	Total Ixezumab Total	Total IXE Total	IXE80Q2W vs. PBO
	Safety Population	Add the following treatment groups for analyses evaluating the impact of ixekizumab starting dose: Ixezumab 80 mg Q4W / 80 mg Starting Dose Ixezumab 80 mg Q4W / 160 mg Starting Dose Ixezumab 80 mg Q2W / 80 mg Starting Dose Ixezumab 80 mg Q2W / 160 mg Starting Dose Total Ixezumab / 80 mg Starting Dose Total Ixezumab / 160 mg Starting Dose	IXE80Q4W/80S ^b IXE80Q4W/160S ^b IXE80Q2W/80S ^b IXE80Q2W/160S ^b Total IXE/80S ^b Total IXE/160S ^b	Overall ^a IXE80Q4W/80S ^b vs. IXE80Q4W/160S ^b ; IXE80Q2W/80S ^b vs. IXE80Q2W/160S ^b ; Total IXE/80S ^b vs. Total IXE/160S ^b
Extended Treatment Period (Period 3)	Extended Treatment Period Population	Placebo/Ixezumab 80 mg Q4W Placebo/Ixezumab 80 mg Q2W Adalimumab 40Q2W / Ixezumab 80 mg Q4W Adalimumab 40Q2W / Ixezumab 80 mg Q2W Ixezumab 80 mg Q4W / Ixezumab 80 mg Q4W Ixezumab 80 mg Q2W / Ixezumab 80 mg Q2W Placebo/Ixezumab 80 mg Adalimumab 40Q2W /Ixezumab 80 mg Ixezumab 80 mg / Ixezumab 80 mg Total Ixezumab 80 mg Q4W ^c Total Ixezumab 80 mg Q2W ^c Total	PBO/IXE80Q4W PBO/IXE80Q2W ADA40Q2W/IXE80Q4W ADA40Q2W/IXE80Q2W IXE80Q4W/IXE80Q4W IXE80Q2W/IXE80Q2W PBO/IXE ADA40Q2W/IXE IXE/IXE Total IXE80Q4W Total IXE80Q2W Total	No Between-Group or Overall Comparisons
Extended Treatment Period	Adalimumab Washout Population	Adalimumab 40 mg Q2W	ADA40Q2W	NA

Study Period	Analysis Population	Treatment Group	Abbreviation	Comparison
(Period 3)				
Combined Periods 2 and 3	Intent-to-Treat Population Who are Initially Randomized to Ixekizumab	Ixekizumab 80 mg Q4W Ixekizumab 80 mg Q2W Total Ixekizumab	IXE80Q4W IXE80Q2W Total IXE	No Between-Group or Overall Comparisons
Combined Periods 2 and 3	Safety Population Who are Initially Randomized to Ixekizumab	Ixekizumab 80 mg Q4W Ixekizumab 80 mg Q2W Total Ixekizumab	IXE80Q4W IXE80Q2W Total IXE	No Between-Group or Overall Comparisons

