Combined Periods 2 and 3 (on Ixekizumab treatment only)	All Ixekizumab Exposures Safety Population ^e	Ixekizumab 80 mg Q4W Ixekizumab 80 mg Q2W Total Ixekizumab	IXE80Q4W IXE80Q2W Total IXE	No Between-Group or Overall Comparisons
Post-Treatment Follow-up Period (Period 4) ^d	Follow-Up Population	Placebo Adalimumab 40 mg Q2W Ixekizumab 80 mg Q4W Ixekizumab 80 mg Q2W Total Ixekizumab Total	PBO ADA40Q2W IXE80Q4W IXE80Q2W Total IXE Total	No Between-Group or Overall Comparisons

Abbreviations: ADA = adalimumab; IXE80Q2W = ixekizumab 80 mg every 2 weeks; IXE80Q4W = ixekizumab 80 mg every 4 weeks PBO = placebo; Q2W = every 2 weeks; Q4W = every 4 weeks.

- a Overall comparison will be conducted for demographics, historical illness, medical history, preexisting condition, and previous therapy. The between-group comparisons and the overall comparison will be conducted for concomitant therapy, compliance, disposition, and safety.
- b S = starting dose; differences between starting dose groups and 95% CI will be provided.
- c For Extended Treatment Period Population, ‘Total Ixekizumab 80 mg Q4W’ is a pooled group of ‘Placebo/Ixekizumab 80 mg Q4W’, ‘Adalimumab 40Q2W/Ixekizumab 80 mg Q4W’ and ‘Ixekizumab 80 mg Q4W/Ixekizumab 80 mg Q4W’; similarly, ‘Total Ixekizumab 80 mg Q2W’ is a pooled group of ‘Placebo/Ixekizumab 80 mg Q2W’, ‘Adalimumab 40Q2W /Ixekizumab 80 mg Q2W’ and ‘Ixekizumab 80 mg Q2W/Ixekizumab 80 mg Q2W’.
- d Treatment group refers to the treatment regimen that the patient received prior to entering Period 4.
- e defined as all patients who received at least one dose of ixekizumab during the study

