Healthcare Resource Utilization	Visits to medical care provider; Days in Hospital; Number of hospital admissions; Healthcare provider	Descriptive statistics	ITT Population	overall comparison in Period 2 by Kruskal Wallis test
		Descriptive statistics	Extended Treatment Period Population	IXE80Q2W & IXE80Q4W during Period 3

Abbreviations: ANCOVA = analysis of covariance; EQ-5D-5L = European Quality of Life – 5 Dimensions 5 Level; ITT = intent-to-treat; IXE80Q2W = ixekizumab 80 mg every 2 weeks; IXE80Q4W = ixekizumab 80 mg every 4 weeks; mBOCF = modified baseline observation carried forward; NRI = nonresponder imputation; UK = United Kingdom; VAS = visual analog scale.

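### The only test named for healthcare resource use in Period 2 is an overall Kruskal-Wallis test, which cannot attribute a difference to either ixekizumab regimen

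*SAP*

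**What the plan says.** SAP 6.17 sets the exploratory objective: "To explore the impact of each ixekizumab regimen on change from baseline in measures of health utility (EQ-5D); and healthcare resource utilization", in the double-blind period and the extension.

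Table RHBV.6.15 (SAP 6.17.4) turns this into analyses. For resource utilization in the ITT Population, the method column says descriptive statistics and the comparison column says "overall comparison in Period 2 by Kruskal Wallis test". The row covers visits to medical care providers, days in hospital, number of hospital admissions, and healthcare provider. Table RHBV.6.14 describes the last of these as "Healthcare providers (type of specialist for healthcare practitioner").

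The EQ-5D rows of the same table serve the same objective and name the contrast directly: "IXE80Q2W & IXE80Q4W vs. placebo at Week 16".

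Three other places bear on the point:

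- SAP 6.1.1 says that comparisons of each ixekizumab regimen with placebo, "as well as comparisons between adalimumab and placebo, will be performed for all analyses in Period 2". Protocol 9.2.1 has the same rule, beginning "Comparisons between each ixekizumab regimen (80 mg Q2W or 80 mg Q4W) and placebo".
- SAP Table RHBV.6.2 lists the randomized Period 2 groups as "Placebo Adalimumab 40 mg Q2W Ixezumab 80 mg Q4W Ixezumab 80 mg Q2W".
- Footnote a of that table says where overall comparisons apply: "Overall comparison will be conducted for demographics, historical illness, medical history, preexisting condition, and previous therapy". It adds concomitant therapy, compliance, disposition and safety, and there the overall test comes with between-group comparisons. Resource utilization is not on either list.

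**The concern.** The question is about each ixekizumab regimen, but the named test asks whether any arm differs from any other. Adalimumab is in the trial as an approved active control to show assay sensitivity. If resource use follows disease activity, the overall null may be false because of adalimumab alone.

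A significant p-value in the resource-use table could then be reported as an ixekizumab effect when the test gives no basis for that. A reader who wants the regimen-specific answer finds a general rule promising it, but no row that delivers it and no method to apply. The programmer would have to choose one.

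A smaller issue concerns the healthcare provider variable. If it is analysed as a specialist category, ranking it has no meaning, because the result depends on how the categories are numbered.

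**Working it through.** **The plan's own figures.** The documents give no rate, variance or power for resource use. Their only design figure is for ASAS40: 80 per arm, 44% versus 16%, two-sided Fisher's exact test at 0.05, about 96% power. Exact enumeration gives 96.7%, which agrees. The arm size of 80 is carried forward.

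**Why attribution fails.** This step needs no assumption about counts. With four arms of n = 80, N = 320 and, apart from the common tie correction,

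H = [12 / (N(N+1))] × Σ n (R̄ⱼ − (N+1)/2)²

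= [12 × 80 / (320 × 321)] × Σ (R̄ⱼ − 160.5)²

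= 0.00935 × Σ (R̄ⱼ − 160.5)²,

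where R̄ⱼ is the mean rank in arm j, on 4 − 1 = 3 degrees of freedom. The sum treats all arms alike. If the adalimumab and Q2W labels are exchanged, H and its p-value do not change, so the statistic carries no information on which arm departs.

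**Illustration.** Inputs that are assumptions: negative binomial counts, with placebo mean 0.5, 1 or 2, dispersion k of 0.5, 1 or 2, and an affected arm at half the placebo mean. There were 2,000 simulated trials per scenario. Each cell gives the range in % over the nine combinations, with the value at mean 1, k = 1 in brackets.

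| Assumed truth | Overall, four arms | Q2W vs placebo | Q4W vs placebo | Adalimumab vs placebo |
|---|---|---|---|---|
| No arm differs | 4.2–5.9 (4.7) | 4.4–6.2 (4.4) | 4.2–5.8 (5.0) | 4.4–5.8 (4.8) |
| Adalimumab alone halved | 38.2–97.2 (73.0) | 4.5–5.6 (5.2) | 4.9–5.7 (5.0) | 40.4–94.8 (70.8) |
| Q2W alone halved | 35.0–97.5 (74.2) | 40.0–94.6 (71.4) | 4.3–6.0 (4.9) | 4.0–6.2 (5.6) |

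The pairwise columns are Wilcoxon rank-sum tests. Simulation error near 5% is √(0.05 × 0.95 / 2,000), about 0.5 points.

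The table shows three things:

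1. The overall test holds its level when no arm differs.
2. The second and third rows look alike in the overall column (73.0% and 74.2% in brackets) but are clearly separated in the pairwise columns.
3. Little power is lost by looking pairwise. With Q2W alone affected, across the nine combinations its Wilcoxon test ranges from 4.4 points below the overall test (81.8% against 86.2%) to 5.0 points above it (40.0% against 35.0%).

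**The case against.** The strongest reply is that the general rule already covers this. SAP 6.1.1 and protocol 9.2.1 require the pairwise comparisons in all Period 2 analyses, and nothing in the row cancels that. This stands to an extent. A reader might infer that the regimen-specific question is never tested, and the documents do not support that. What they show is a row that does not carry out the rule and a missing pairwise method.

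Second, the objective is to explore, no hypothesis is stated, and descriptive statistics by arm are planned. This also stands. It would be too strong to say that the plan cannot address the objective; the limitation belongs to the named test.

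Third, rejection rates of 38% to 97% might be taken as a false-positive rate far above 5%. They are not. When adalimumab differs, the overall null is false and rejecting it is correct, so these figures are power. The test is valid for the question it asks. It can also be the more powerful one: with both ixekizumab arms halved, at mean 1 and k = 1, it rejects in 85.5% of trials, against 70.4% (Q2W) and 70.3% (Q4W) for the pairwise tests. That is a reason to keep it.

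Fourth, the row says only that the comparison is overall; four arms is inferred from Table RHBV.6.2. If adalimumab were left out, the three-arm test would reject in 4.3% to 5.5% of trials when adalimumab alone differs. It would still not separate Q2W from Q4W.

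Finally, the SAP does not say how healthcare provider is coded. Visit counts by specialist type could be ranked, so that point is conditional.

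**Conclusion.** The concern holds as a mismatch between the row and its objective. The only inferential comparison named for resource use in Period 2 is an overall test. Given the Period 2 arms, its rejection cannot be attributed to either ixekizumab regimen. The row also differs from the EQ-5D rows beside it, does not implement the rule in SAP 6.1.1 and protocol 9.2.1, and leaves the pairwise method unspecified.

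The attribution argument follows from the form of the statistic. The percentages are illustrative only: they rest on assumed count distributions, and means of 0.5 to 2 may not represent days in hospital or admissions. No error-rate inflation is claimed.

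The consequence is small. The analysis is exploratory and outside the graphical testing procedure, and no primary or major secondary conclusion depends on it.

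**What to change.** In the Period 2 resource-utilization row of Table RHBV.6.15:

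- For provider visits, days in hospital and admissions, add Wilcoxon rank-sum comparisons of Q2W with placebo and of Q4W with placebo, and show adalimumab against placebo separately.
- Keep the overall Kruskal-Wallis test as supplementary, and state which arms it includes.
- State how healthcare provider is analysed. If it is a type of specialist, report the proportion of patients with any visit to each type and compare by Fisher's exact test instead of a rank test.

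This needs no new data, only table wording. The cost is more unadjusted exploratory p-values: 3 variables × 2 contrasts = 6, or 3 × 3 = 9 if adalimumab is also tested, plus the Fisher tests for any provider types. SAP 6.5 already makes no multiplicity adjustment outside the primary and major secondary objectives. The SAP revision history records that Version 3 was approved after unblinding. If the method is added later than that, it should be labelled as specified after unblinding, although the contrasts themselves follow the existing rule in SAP 6.1.1.
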